Appendix E: Response Evaluation Criteria in Solid Tumors (RECIST) Version 1.1

Definitions

Response and progression will be evaluated in this study using the Response Evaluation Criteria in Solid Tumors (RECIST) version 1.1 (Eisenhauer et al 2009). Lesions are either measurable or non-measurable using the criteria provided below. The term “evaluable” in reference to measurability will not be used, as it does not provide additional meaning or accuracy.

Baseline Eligibility

Measurable Disease:	
Tumor lesions: Must be accurately measured in at least one dimension (longest diameter in the plane of measurement is to be recorded) with a minimum size of:
 
• 10 mm by CT by computerized tomography (CT scan slice thickness no greater than 5 mm).• 10 mm caliper measurement by clinical exam (lesions that cannot be accurately measured with calipers should be recorded as non-measurable).• 20 mm by chest x-ray. 
Skin lesions: Documentation by color photography, including a ruler to estimate the size of the lesion, is recommended.
 
Malignant lymph nodes: To be considered pathologically enlarged and measurable, a lymph node must be ≥ 15 mm in short axis when assessed by CT scan. At baseline and in follow-up, only the short axis will be measured and followed.

Non-Measurable Disease:	All other lesions, including small lesions (longest diameter $<<10$ mm or pathological lymph nodes with ≥ 10 - to $<<15$ -mm short axis) as well as truly non-measurable lesions. Lesions considered truly non-measurable include: leptomeningeal disease, ascites, pleural or pericardial effusion, inflammatory breast disease, lymphangitic involvement of skin or lung, abdominal masses, abdominal organomegaly identified by physical exam that is not measurable by reproducible imaging techniques.
Target Lesions:	
The most reproducible measurable lesions, up to a maximum of 2 lesions per organ and 5 lesions in total, representative of all involved organs should be identified as target lesions and recorded and measured at baseline.
 
Target lesions should be selected on the basis of their size (lesions with the longest diameter), should be representative of all involved organs, and in addition should be those that lend themselves to reproducible repeated measurements. Pathological nodes which are defined as measurable and that may be identified as target lesions must meet the criterion or a short axis of ≥ 15 mm by CT scan.
 
A sum of the diameters (longest for non-nodal lesions, short axis for nodal lesions) for all target lesions will be calculated and reported as the baseline sum diameters. If lymph nodes are to be included in the sum, then as noted above, only the short axis is added into the sum. The baseline sum diameters will be used as reference to further characterize any objective tumor response.

Non-Target Lesions:	
All other lesions should be identified as non-target lesions at baseline. Measurements of these lesions are not required, but the presence or absence of each should be noted throughout follow-up.

CONFIDENTIAL

STUDY DRUG(S): EVEROLIMUS
FINAL PROTOCOL DATE: 19 JUNE 2014

SCRI INNOVATIONS STUDY NUMBER: BRE 212
VERSION 1.0

Guidelines for Evaluation of Measureable Disease

All measurements should be taken and recorded in metric notation, using a ruler or calipers. All baseline evaluations should be performed as closely as possible to the beginning of treatment, as per protocol screening requirements.

The same method of assessment and the same technique should be used to characterize each identified and reported lesion at baseline and during follow-up. Imaging-based evaluation is preferred to evaluation by clinical examination when both methods have been used to assess the anti-tumor effect of a treatment.

Clinical Lesions:	Clinical lesions will only be considered measurable when they are superficial (e.g., skin nodules and palpable lymph nodes) and ≥ 10 mm in diameter. In the case of skin lesions, documentation by color photography, including a ruler to estimate the size of the lesion, is recommended.
Chest X-ray:	Lesions on chest X-ray are acceptable as measurable lesions when they are clearly defined and surrounded by aerated lung. However, a CT scan is preferable.
Conventional CT and MRI:	CT, MRI: CT is the best currently available and reproducible method to measure lesions selected for response assessment. This guideline has defined measurability of lesions on CT scan based on the assumption that CT slice thickness is 5mm or less. When CT scans have slice thickness greater than 5 mm, the minimum size for a measurable lesion should be twice the slice thickness. MRI is also acceptable in certain situations (e.g. for body scans).
Ultrasound:	When the primary study endpoint is objective response, ultrasound should not be used to measure tumor lesions. It is, however, a possible alternative to clinical measurements of superficial palpable lymph nodes, subcutaneous lesions, and thyroid nodules. Ultrasound may also be useful to confirm the complete disappearance of superficial lesions usually assessed by clinical examination.
Endoscopy and Laparoscopy:	Use of endoscopy and laparoscopy for objective tumor evaluation has not yet been fully and widely validated. Therefore, use of these techniques for objective tumor response should be restricted to validation purposes in specialized centers. Such techniques can be useful in confirming complete pathological response when biopsies are obtained.
Tumor Markers:	Tumor markers alone cannot be used to assess response. If markers are initially above the upper limit of normal, they must normalize for a subject to be considered in complete clinical response when all lesions have disappeared.
Cytology and Histology:	Cytology and histology can be used to differentiate between partial response (PR) and complete response (CR) in rare cases (e.g., after treatment to differentiate between residual benign lesions and residual malignant lesions in tumor types such as germ cell tumors).

CONFIDENTIAL

STUDY DRUG(S): EVEROLIMUS
FINAL PROTOCOL DATE: 19 JUNE 2014

SCRI INNOVATIONS STUDY NUMBER: BRE 212
VERSION 1.0

Response Criteria

Evaluation of Target Lesions

Complete Response (CR):	Disappearance of all target lesions.
Partial Response (PR):	At least a 30% decrease in the sum of diameters of target lesions, taking as reference the baseline sum diameters..
Stable Disease (SD):	Neither sufficient shrinkage to qualify for PR nor sufficient increase to qualify for PD, taking as reference the smallest (nadir) sum of diameters since the treatment started.
Progressive Disease (PD):	At least a 20% increase in the sum of the diameters of target lesions, taking as reference the smallest (nadir) sum since the treatment started, or the appearance of one or more new lesions. Requires not only 20% increase, but absolute increase of a minimum of 5 mm over sum.

Evaluation of Non-Target Lesions

Complete Response (CR):	Disappearance of all non-target lesions and normalization of tumor markers. All lymph nodes must be non-pathological in size (<<10 mm short axis).
Stable Disease (SD):	Persistence of one or more non-target lesions and/or persistence of tumor marker level above the normal limits.
Progressive Disease (PD):	Appearance of one or more new lesions and/or unequivocal progression of existing non-target lesions. When the subject also has measurable disease, to achieve “unequivocal progression” on the basis of the non-target disease, there must be an overall level of substantial worsening in non-target disease such that, even in presence of SD or PR in the target disease, the overall tumor burden has increased sufficiently to merit discontinuation of therapy.

Evaluation of Best Overall Response

As detailed above, the best overall response is the best response recorded from the start of the treatment until disease progression/recurrence (taking as reference for PD the smallest measurements recorded since the treatment started). In general, the subject's best response assignment will depend on the achievement of both measurement and confirmation criteria.

Confirmation of response (by repeat scans after 4 weeks or as specified in the protocol) is required for studies in which response rate is the primary endpoint, but is not required in randomized studies or studies with primary survival endpoints (i.e., where response is not a primary endpoint).

CONFIDENTIAL

STUDY DRUG(S): EVEROLIMUS
FINAL PROTOCOL DATE: 19 JUNE 2014

SCRI INNOVATIONS STUDY NUMBER: BRE 212
VERSION 1.0

Target Lesions	Non-Target Lesions	New Lesions	Overall Response
CR	CR	NO	CR
CR	SD	NO	PR
CR	NE	NO	PR
PR	SD OR NE	NO	PR
SD	SD OR NE	NO	SD
PD	ANY	YES OR NO	PD
ANY	PD	YES OR NO	PD
ANY	ANY	YES	PD

In some circumstances, it may be difficult to distinguish residual disease from normal tissue. When the evaluation of a CR depends upon this determination, it is recommended that the residual lesion be investigated by fine needle aspirate or biopsy to confirm the CR status.

When nodal disease is included in the sum of target lesions, and the nodes decrease to “normal” size (<<10 mm), they may still have a measurement reported on scans. This measurement should be recorded even though the nodes are normal in order not to overstate progression, should it be based on increase in size of the nodes. As noted earlier, this means that subjects with CR may not have a total sum of “zero” on the eCRF.

CONFIDENTIAL

STUDY DRUG(S): EVEROLIMUS
FINAL PROTOCOL DATE: 19 JUNE 2014

SCRI INNOVATIONS STUDY NUMBER: BRE 212
VERSION 1.0

Appendix F: Clinically Relevant Drug Interactions of CYP3A and PgP

Clinically relevant drug interactions: inducers, and inhibitors of isoenzyme CYP3A

Inducers

Strong inducers:

avasimibe, carbamazepine, mitotane, phenobarbital, phenytoin, rifabutin, rifampin (rifampicin), St. John's wort, (hypericum perforatum)

Moderate inducers:

bosentan, efavirenz, etravirine, genistein, modafinil, naftillin, ritonavir, [talviraline], thioridazine, tipranavir

Weak inducers:

amprenavir, aprepitant, armodafinil (R-modafinil), bexarotene, clobazam, danshen, dexamethasone, Echinacea, garlic (allium sativum), gingko (ginkgo biloba), glycyrrhizin, methylprednisolone, nevirapine, oxcarbazepine, pioglitazone, prednisone, [pleconaril], primidone, raltegravir, rufinamide, sorafenib, telaprevir, terbinafine,

Inhibitors

Strong inhibitors:

boceprevir, clarithromycin, cobicistat, conivaptan, elvitegravir, indinavir, itraconazole, ketoconazole, lopinavir, mibefradil, nefazodone, neflifinavir, posaconazole (Krishna et al 2009), ritonavir, saquinavir, telaprevir, telithromycin, tipranavir, troleandomycin, voriconazole

Moderate inhibitors:

Amprenavir, aprepitant, atazanavir, casopitant, cimetidine, ciprofloxacin, cyclosporine, darunavir, diltiazem, dronedarone, erythromycin, fluconazole, fosamprenavir, grapefruit juice (citrus parasida fruit juice), imatinib, schisandra sphenanthera, tofisopam, verapam

CONFIDENTIAL

STUDY DRUG(S): EVEROLIMUS
FINAL PROTOCOL DATE: 19 JUNE 2014

SCRI INNOVATIONS STUDY NUMBER: BRE 212
VERSION 1.0

Clinically relevant drug interactions: substrates, inducers, inhibitors of PgP and PgP/CYP3A dual inhibitors

Substrates

colchicine, digoxin, fexofenadine, indinavir, paclitaxel, talinolol, topotecan, vincristine, everolimus

Inducers

rifampin, St John's wort

PgP Inhibitors and PgP/CYP3A Dual Inhibitors

amiodarone, azithromycin, captopril, carvedilol, clarithromycin, conivaptan, diltiazem, dronedarone, elacridar, erythromycin, felodipine, fexofenadine, fluvoxamine, ginkgo (ginkgo biloba), indinavir, itraconazole, lopinavir, mibepradil, milk thistle (silybum marianum), nelfinavir, nifedipine, nitrendipine, paroxetine, quercetin, quinidine, ranolazine, rifampin, ritonavir, saquinavir, Schisandra chinensis, St John's wort (hypericum perforatum), talinolol, Telaprevir, telmisartan, ticagrelor, tipranavir, tolvaptan, valsartan, verapamil

Reference: Internal Clinical Pharmacology Drug-drug interaction (DDI) memo, updated Oct. 2, 2011, 29-Oct-2012 which summarizes DDI data from three sources including the FDA's "Guidance for Industry, Drug Interaction Studies", the University of Washington's Drug Interaction Database, and Indiana University School of Medicine's Drug Interaction Table

CONFIDENTIAL

STUDY DRUG(S): EVEROLIMUS
FINAL PROTOCOL DATE: 19 JUNE 2014

SCRI INNOVATIONS STUDY NUMBER: BRE 212
VERSION 1.0

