5.5 CYP3A4 and/or PgP Inhibitors/Inducers/Substrates

Everolimus is metabolized by CYP3A4 in the liver and to some extent in the intestinal wall. Therefore, the following are recommended:

- Co-administration with strong inhibitors of CYP3A4 (e.g., ketoconazole, itraconazole, ritonavir) or P-glycoprotein (PgP) inhibitor should be avoided.
- Co-administration with moderate CYP3A4 inhibitors (e.g. erythromycin, fluconazole) or PgP inhibitors should be used with caution. If a patient requires co-administration of moderate CYP3A4 inhibitors or PgP inhibitors, reduce the dose of everolimus by approximately 50%. Additional dose reductions to every other day may be required to manage toxicities. If the inhibitor is discontinued, the everolimus dose should be returned to the dose used prior to initiation of the moderate CYP3A4/PgP inhibitor after a washout period of 2 to 3 days.
- Grapefruit or citrus juices affect P450 and PgP activity; therefore, concomitant use should be avoided.
- If patients require co-administration of a strong CYP3A4 inducer, consider doubling the daily dose of everolimus (based on pharmacokinetic data), using increments of 5 mg or less. This dose of everolimus is predicted to adjust the AUC to the range observed without inducers. However, there are no clinical data with this dose adjustment in patients receiving strong CYP3A4 inducers. If the strong inducer is discontinued, consider a washout period of at least 3 to 5 days (reasonable time for significant enzyme de-induction), before the everolimus dose is returned to the dose used prior to initiation of the strong CYP3A4 inducer.
- This dose adjustment of everolimus is intended to achieve similar AUC to the range observed without inducers. However, there are no clinical data with this dose adjustment in patients receiving strong CYP3A4 inducers. If the strong inducer is discontinued the everolimus dose should be returned to the dose used prior to initiation of the strong CYP3A4/PgP inducer.
- Oral contraceptives in preclinical and clinical data have shown everolimus to have CYP3A4 inhibitory activity rather than induction activity; induction of metabolism of contraceptive hormones by everolimus is unlikely. Consequently, administration of everolimus should not reduce the efficacy of oral contraceptives.

Refer to the listing of relevant inducers and inhibitors of CYP3A4 and the list of relevant substrates, inducers and inhibitors of PgP in Appendix E.

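### Section 5.5 attaches opposite everolimus adjustments to two Appendix F lists that both contain rifampin and St John's wort, and does not say which list governs

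*Protocol*

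**What the plan says.** Appendix F of the protocol holds the lookup lists for drug interactions. Rifampin and St John's wort appear there three times:

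- among the strong CYP3A inducers: "phenytoin, rifabutin, rifampin (rifampicin), St. John's wort, (hypericum perforatum";
- as the whole of the PgP inducer list: "rifampin, St John's wort";
- in the combined list of PgP inhibitors and dual PgP/CYP3A inhibitors: "nitrendipine, paroxetine, quercetin, quinidine, ranolazine, rifampin, ritonavir, saquinavir, Schisandra chinensis", followed directly by St John's wort.

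Section 5.5 turns list membership into dosing advice. For the inhibitor side: "If a patient requires co-administration of moderate CYP3A4 inhibitors or PgP inhibitors, reduce the dose of everolimus by approximately 50" (per cent). For the inducer side: "If patients require co-administration of a strong CYP3A4 inducer, consider doubling the daily dose of everolimus", in steps of no more than 5 mg, with the remark that no clinical data support the adjustment.

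On stopping a strong inducer, one bullet says "consider a washout period of at least 3 to 5 days (reasonable time for significant enzyme de-induction), before the everolimus dose is returned" to its earlier level. The next bullet says "If the strong inducer is discontinued the everolimus dose should be returned to the dose used prior to initiation of the strong CYP3A4/PgP inducer" and gives no timing.

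Two other statements bear on the point. Exclusion criterion 10 (Section 3.2 and the synopsis) bars strong CYP3A4 inhibitors and inducers from 72 hours before study treatment through to the end of everolimus, and refers the reader to Section 5.5. The first bullet of Section 5.5 says that PgP inhibitors should be avoided.

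**The concern.** Section 5.5 works only if a drug's list tells the site what to do. For rifampin and St John's wort it does not: one listing leads to a lower everolimus dose, another to consideration of a higher one, and no rule ranks them. Section 5.5 itself says that the increase for inducers is meant to restore the usual AUC, so an adjustment in the wrong direction would move exposure away from the intended range.

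The case is foreseeable. Section 5.4 asks patients to consult the investigator before taking any additional medication, over-the-counter products included. Section 5.5 and Appendix F are what an investigator would then open. The stake is the safety and consistency of individual dosing, not the primary PFS analysis.

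**Working it through.** The plan states no figure to reproduce. The check sets the lists against the rules and applies the two stated multipliers to the starting dose.

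1. **Overlap of the lists.** Appendix F names eight strong CYP3A inducers: avasimibe, carbamazepine, mitotane, phenobarbital, phenytoin, rifabutin, rifampin and St John's wort. Of these, two (rifampin and St John's wort) also stand on the PgP inhibitor list; the other six do not.

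2. **Which overlaps matter.** Other drugs also sit on an inducer list and an inhibitor list: ritonavir and tipranavir (moderate inducers, strong inhibitors), telaprevir (weak inducer, strong inhibitor), amprenavir and aprepitant (weak inducers, moderate inhibitors). Section 5.5 attaches a dose increase only to strong inducers, so these drugs do not receive opposite adjustments. The conflict is confined to the two drugs in step 1.

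3. **Size of the gap.** Starting dose 10 mg daily (Section 5.1.1).
 - PgP inhibitor rule: 10 mg × 0.5 = about 5 mg daily.
 - Strong inducer rule: 10 mg × 2 = 20 mg daily, as a ceiling.
 - Ratio at the extremes: 20 / 5 = 4.

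 The lower figure is approximate because the reduction is. The upper figure is a maximum, because doubling is only to be considered and is approached in limited steps.

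4. **Precedence.** Neither Section 5.5 nor Appendix F says which list governs a drug that is on both.

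5. **Is the situation allowed to arise?**
 - Exclusion criterion 10: no strong inducer during everolimus treatment.
 - Section 5.5, first bullet: avoid PgP inhibitors.
 - Section 5.5, second bullet: PgP inhibitors with caution, and a reduction if one is required.
 - Section 5.5, inducer bullet: an adjustment if a strong inducer is required.

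 The first two statements close the door; the last two give instructions for patients who have gone through it.

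6. **Return to the earlier dose.** The two adjacent inducer bullets repeat the same remarks on AUC and on the lack of clinical data. One adds a washout of at least 3 to 5 days to consider; the other is silent on timing. The PgP inhibitor bullet gives a washout of 2 to 3 days, so a drug on both lists also lacks a single instruction at this step.

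7. **Pointers.** Section 5.5 twice sends the reader to Appendix E for the lists: at the end of its bullets, and under its sub-heading on drugs that influence CYP3A4. Appendix E is RECIST; the lists are in Appendix F, as the list of appendices correctly shows.

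**The case against.** The strongest reply is that the conflict should not be reached. Both drugs are on the strong inducer list, so exclusion criterion 10 rules them out; the inhibitor listing leads first to an instruction to avoid. Either way, the first message is not to co-administer. This stands as a limit on frequency. It does not remove the problem, because criterion 10 refers to Section 5.5, and Section 5.5 provides for patients who require such a drug.

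Three stronger readings are tempting, and the documents do not support them.

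- A reader might infer that Appendix F is itself wrong to list a drug as both inducer and inhibitor. The appendix summarises drug properties from three sources, its lists are not mutually exclusive, and several other drugs appear on two. The entries may be deliberate; the source memo is not available here. What is missing is a precedence rule.
- A reader might take 20 mg daily as what the protocol prescribes. The text asks only that doubling be considered, in limited steps.
- A reader might take the second inducer bullet to mean an immediate return to the earlier dose. It says nothing on timing, and a site can follow both bullets together. They are an unmerged duplicate, not two opposed schedules.

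The wrong appendix letter is clerical.

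**Conclusion.** The point holds as a minor internal inconsistency in dosing instructions. For rifampin and St John's wort, Section 5.5 read with Appendix F supports adjustments in opposite directions, with no stated order between them. At the extremes the readings differ by up to four-fold (about 5 mg against at most 20 mg daily from a 10 mg start). Exclusion criterion 10 and the permissive bullets of Section 5.5 are also not aligned with each other.

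The documents give no expected number of affected patients. That it will be very few is an assumption, resting on criterion 10 and on the advice to avoid PgP inhibitors; each such patient would be 1/46, about 2.2% of planned enrolment. On that assumption the primary PFS result is not materially threatened. No view is taken on which classification, adjustment or washout is right.

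**What to change.** The sponsor should:

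- reconcile exclusion criterion 10, Section 5.5 and Appendix F so that a drug on more than one list leads to a single instruction, either by revising the lists or by stating which list governs;
- say whether the Section 5.5 provisions for required strong inducers and PgP inhibitors stand alongside criterion 10 and the advice to avoid, and in what circumstances;
- merge the two inducer bullets into one statement on return to the prior dose;
- change both Appendix E pointers in Section 5.5 to Appendix F.

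The clinical content is for the sponsor to decide. The cost is a short protocol clarification with the usual review: one criterion, a few bullets and one appendix. Sample size, endpoints and analyses are untouched.

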Appendix G: VeriStrat® Assay

VeriStrat is a pre-treatment blood-based test correlated with clinical outcome after epidermal growth factor receptor (EGFR)-tyrosine kinase inhibitor (TKI) therapy in patients with NSCLC. VeriStrat was developed in a multi-institutional study of advanced NSCLC patients treated with gefitinib¹. The VeriStrat algorithm was developed using a training set of pre-treatment serum samples from patients who experienced either long term stable disease or early progression on gefitinib therapy. Mass spectra (MS) from these patients' serum samples were used to define 12 MS features (i.e. peaks), differentiating these two outcome groups. VeriStrat was created by utilizing eight of these features based on a *k*-nearest neighbors (KNN) classification scheme and its parameters optimized using additional spectra from the training cohort. All aspects of the algorithm were permanently frozen after development. VeriStrat assigns patient samples a classification of VeriStrat Good (VS-G) or VeriStrat Poor (VS-P).

VeriStrat was validated in a blinded fashion on the pre-treatment serum of two independent cohorts of patients who were treated with gefitinib or erlotinib (an EGFR-TKI)¹. These studies confirmed that patients classified as VS-G had better outcomes than patients classified as VS-P (Hazard Ratio [HR] of death=0.50 *P*=0.0054 in one cohort, HR of death=0.40 *P*≤0.001 in the other). VeriStrat was shown to correlate with clinical outcome following EGFR-TKI therapy, but not following chemotherapy or post-surgery as there was no statistically significant difference seen in the overall survival of patients classified as VS-G or VS-P before second-line chemotherapy (HR=0.74, 95%, *P*=0.42 in one cohort and HR=0.81, *P*=0.54 in another). In a third control cohort of patients with resected early-stage NSCLC, the HR for overall survival was 0.90 (*P*=0.79).

Retrospective analysis of VeriStrat testing performed on available serum samples of a subset of patients from the BR 21 trial (second or third line NSCLC patients randomized to erlotinib or placebo), demonstrated evidence of a significant prognostic component of the VeriStrat test, and indicated a strong statistically significant correlation of the VS-G label with objective response rate (ORR) and disease control rate (DCR) in the treatment arm (Fisher exact test 2-sided *p* value 0.0022 for ORR and *p* value <0.001 for DCR)². Importantly, this study also demonstrated the independence of VeriStrat classification from known genetic markers (i.e., *EGFR* mutations, *EGFR* amplification [by FISH], and *KRAS* mutations).

Finally, VeriStrat was prospectively validated in the Randomized Proteomic Stratified Phase III Study of Second Line Erlotinib versus Chemotherapy in Patients with Inoperable Non-Small Cell Lung Cancer (PROSE)³. PROSE is the world's first completed prospective biomarker-stratified study in oncology to test treatment and biomarker interaction. This is a multi-center, randomized, Phase 3 study of 285 study patients with advanced NSCLC who have progressed after first line chemotherapy treatment. Patients were randomized 1:1 to receive either standard dose erlotinib or chemotherapy (dealer's choice, pemetrexed or docetaxel), and stratified by ECOG Performance Status, smoking status, and blinded pre-treatment VeriStrat classification. PROSE results show that patients classified as VS-G have similar OS when treated with either

CONFIDENTIAL

STUDY DRUG(S): EVEROLIMUS
FINAL PROTOCOL DATE: 19 JUNE 2014

SCRI INNOVATIONS STUDY NUMBER: BRE 212
VERSION 1.0

erlotinib or chemotherapy, whereas patients classified as VS-P have better OS on chemotherapy compared with erlotinib. The study reached its primary objective of showing significant interaction between treatment outcome and VeriStrat classification with an interaction p-value of 0.031. The results confirm that VeriStrat status is predictive of differential overall survival benefit for erlotinib versus chemotherapy in a second-line setting.

Further studies demonstrate that VeriStrat may have clinical utility in various solid epithelial tumors treated with a variety of targeted drugs and their combinations⁴. In head and neck squamous cell carcinoma (HNSCC), VeriStrat was correlated with survival of patients treated with gefitinib (HR=0.41, p=0.007), erlotinib/bevacizumab (HR=0.2, p=0.02), and cetuximab (HR=0.26, p=0.06); a chemotherapy cohort showed no statistically significant survival difference. In a cohort of colorectal cancer (CRC) patients treated with cetuximab, the difference in progression free survival between VS-G and VS-P patients was also significant, with HR=0.51 (p=0.0065).

More recent studies evaluated the effect of VeriStrat stratification on the treatment efficacy of letrozole with or without lapatinib in first line metastatic breast cancer patients in a retrospective analysis of the phase III trial EGF30008⁵. Of the 1286 patients randomized (HER2 positive=219; HER2 negative=952; HER2 unknown=115), 1163 patients had serum available for analysis. A VeriStrat label was assigned to 1046 patients (VS-G=961; VS-P=80; VS Indeterminate=5). In the overall population there was no significant difference in PFS between VS-G and VS-P groups within the letrozole + lapatinib arm (p=0.53). In contrast, PFS of the VS-G group was longer than that of the VS-P group within the letrozole only arm (HR=0.36, p<0.001) and comparable with that of Good patients within the letrozole + lapatinib arm (median PFS 10.8 months vs 11.0 months). In multivariate analysis VeriStrat classification was independently significant in the presence of other clinical variables. A significant interaction between VeriStrat classification and treatment (interaction p=0.002) indicate that the test is not merely prognostic, but predictive with respect to benefit from different treatments. This suggests that the VS-P group may represent primary hormone resistance that is overcome by the addition of lapatinib to letrozole.

In this study an exploratory evaluation of VeriStrat will be conducted. Treatment options for this study will not be based on the results of this testing.

Serum samples for VeriStrat testing will be collected as follows: the investigative site will follow standard of care protocols:

- Baseline visit (pre-treatment)
- Cycle 3, Day 1 visit (prior to treatment)
- At disease progression
- At the first Follow-Up visit after disease progression.

Sample Collection and Processing

1. Use a BRE 212 VeriStrat collection kit for each sample collection.

CONFIDENTIAL

STUDY DRUG(S): EVEROLIMUS
FINAL PROTOCOL DATE: 19 JUNE 2014

SCRI INNOVATIONS STUDY NUMBER: BRE 212
VERSION 1.0

2. Complete 3 BRE 212 study identification labels with BRE 212 Subject ID, visit type and collection date.
3. Place 1 label on each of the following
 - a) 3.5 mL SST (gold-top) Vacutainer tube.
 - b) Serum Collection Card.
 - c) BRE 212 Test Request Form (BRE 212 TRF), upper right corner.
4. Collect venous blood into the 3.5 mL SST Vacutainer.
5. Gently invert the SST 5 times and allow the tube to clot in an upright position for 30 minutes at room temperature (approximately 70°Farenheit or 21°Celcius (C)).
6. Spin the SST in a standard clinical centrifuge at a speed of 1000-1300 gravity (g), or equivalent, for 10-15 minutes. Speed should not exceed 1300 g, and time should not exceed 15 minutes or hemolysis may occur.
7. Verify that the serum is light yellow in color. Pink or reddish serum indicates sample has hemolyzed and must be redrawn.
8. Without disturbing the clot layer, use a transfer pipette to transfer 2 drops (0.1 mL) of serum to each of the 2 circles on the Serum Collection Card.
9. Dispose of SST.
10. Close cover of Serum Collection Card and follow shipping instructions. Sample must be shipped within 24 hours, and may be stored at room temperature until shipping.

Sample Shipment

1. Place the Serum Collection Card into the foil bag and seal.
2. Place the foil bag and the completed, signed BRE 212 TRF into the shipping envelope. Save the yellow copy of the TRF for placement in the subject's study records.
3. Complete the required FedEx® air bill fields, and if shipping on a Friday, check the Saturday delivery box. Remove the sender's copy of the air bill for the subject's study records, and place the remainder of the air bill in the pouch of the shipping envelope.
4. Arrange for and confirm FedEx pickup of the package on the same day as the sample is prepared for shipping.

CONFIDENTIAL

STUDY DRUG(S): EVEROLIMUS
FINAL PROTOCOL DATE: 19 JUNE 2014

SCRI INNOVATIONS STUDY NUMBER: BRE 212
VERSION 1.0

5. Notify Biodesix of pending shipment by emailing a message to [contact]

Include the following in the notification email:

a) Subject: BRE 212 sample shipment

b) Body of message: FedEx tracking number; name and contact information of sender.

Procedures

Upon completion of all serum collection (i.e., all patients have completed the first follow-up visit following end of trial treatment), serum samples will be analyzed using MALDI ToF MS and the VeriStrat results will be sent to SCRI at the completion of the study. Upon unblinding of the clinical data, in accordance with the endpoints described in the trial protocol, statistical analysis will be carried out independently by SCRI and by Biodesix. Biodesix statistical analyses will be performed using SAS 9.2 (Cary, NC) and PRISM (GraphPad, La Jolla, CA).

Statistical Analysis Plan

Since there is no previous information on VeriStrat testing in this population of patients, this study is exploratory in nature. In the retrospective analysis of metastatic breast cancer patients from the EGF30008 study, the VS-P classification was observed in 8-10% of the study population. Assuming a similar rate of occurrence of the VS-P classification, and the planned accrual of 46 subjects, ~4 baseline samples are expected to have a VS-P classification. Based on the lack of previous information on the VeriStrat classification for the patients to be enrolled in this study, no estimation of detectable alternative is provided for the suggested statistical analyses. The feasibility of the statistical analyses will be evaluated after the actual ratio of VS-G/VS-P classification has been determined.

References

CONFIDENTIAL

STUDY DRUG(S): EVEROLIMUS
FINAL PROTOCOL DATE: 19 JUNE 2014

SCRI INNOVATIONS STUDY NUMBER: BRE 212
VERSION 1.0

